9.2 Statistical Analysis

For the primary objective: *To explore the association of hepatic iron content (HIC) measured with the newly developed 1.5T R2*-UTE technique and HIC quantified by liver biopsy in subjects with iron overload.*

The relationship of HIC measured with 1.5T R2*-UTE and quantified by liver biopsy in subjects with iron overload will be explored graphically. If the linear relationship exists, the Pearson's correlation between the HIC measured with 1.5T R2*-UTE technique and the HIC quantified by liver biopsy will be calculated and its 95% confidence interval (CI) will also be reported. If the correlation is sufficiently high, i.e., the lower bound of the 95% CI exceeds 0.7, a simple linear regression model will be established for the HIC prediction. The 95% prediction bounds will be established. If more complicated pattern shown graphically, appropriate model will be developed to describe the relationship.

For the secondary objectives: *To explore the relationship 1) between 1.5T R2*-UTE and 1.5T R2*-GRE measurements in healthy volunteers and in subjects with iron overload and 2) between 1.5T R2*-UTE measurements with iron studies (serum iron and transferrin saturation) in subjects with iron overload.* Analyses will be implemented similarly as the analyses planned in the primary objective to explore the relationships. Pearson's correlation will be used if there is graphical evidence of linear relationship, similarly to the Primary Objective. 95% confidence interval (CI) will also be reported. If correlation is sufficiently high, a simple linear regression model will be developed and the 95% prediction bounds will be established. If more complicated pattern shown graphically, appropriate model will be developed to describe the relationship.

Objectives 1.3.1, 1.3.2, 1.3.3, 1.3.4, and 1.3.5 were classified as exploratory since they do not directly support the future implementation of the 1.5 R2*-UTE technique, and the gathering of the information from variables within these objectives is not yet clear in the near future but may ultimately generate additional hypotheses for future investigation. The purpose of the exploratory objectives is to (1) evaluate how well the R2*-UTE and the R2*-GRE signals correlate in subjects where the R2*-GRE does not fail. The analyses will provide the evidence of whether the R2*-UTE technique can replace the R2*-GRE technique even in the lower HIC

cases. (2) understand the relationships among a set of variables measured, Similar analyses will be implemented similarly to the analyses implemented in the primary objective.

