MIDAS: MASSIVE IRON DEPOSIT ASSESSMENT

Pearson's correlation between the HIC measured with 1.5T R2*-UTE technique and the HIC quantified by liver biopsy will be calculated and its 95% confidence interval (CI) will also be reported. If the correlation is sufficiently high, i.e., the lower bound of the 95% CI exceeds 0.7, a simple linear regression model will be established for the HIC prediction. The 95% prediction bounds will be established. If more complicated pattern shown graphically, appropriate model will be developed to describe the relationship.

Anticipated Study Completion Date: April 2017

Timeframe for Primary Outcome Measure: There will be 2 defined intervals for this study and 1 possible: (I) 1.5 and 3T MRI's, and (II) liver biopsy.

Defined Interval:

1. Screening test with the regular R2*-GRE MRI
 - The new UTE MRI will be done at the same time as the regular R2*-GRE MRI
- OR

2. Liver biopsy

Possible Interval (if liver biopsy not done first, within 30 days):

1. If the regular R2*-GRE MRI can measure the amount of iron in the liver, no other tests will be done.
2. If the regular GRE MRI cannot measure the amount of iron in the liver because the amount of iron is extremely high, a liver biopsy will be recommended to measure the exact amount of iron in the liver.

The primary objective of this study is to compare the results of the new UTE MRI with that of a liver biopsy in research participants with extremely high amounts of iron in the liver.

Data Management: Data collection and data management for this investigation will be conducted through the SJCRH Hematology Department. Co-investigators and CRAs assigned to this protocol will be responsible for assisting the PI in assuring protocol compliance as well as reviewing, transcribing and tracking of all clinical and safety related data.

Human Subjects: MRI does not involve radiation, therefore there are no risks associated with radiation injury. Study participants may need to be sedated for the MRI exam, which may expose the patients to the risks involved with anesthetics and airway complication.

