9.0 STATISTICAL CONSIDERATIONS

This is a non-therapeutic, prospective study aimed to develop a novel R2*-UTE imaging sequence technique to non-invasively and accurately estimate high hepatic iron content (HIC) values (≥ 25 mg Fe/g). The current standard management procedure for patients at risk of iron overload at St. Jude is to estimate their (HIC) by the calibrated R2*-GRE imaging technique, which becomes unreliable when HIC is greater than 25 mg Fe/g. Therefore, the success of the study will provide better monitoring and guidance to the clinical management of patients with massive iron overload.

The primary objective is to test the association of hepatic iron content (HIC) measured with the newly developed 1.5T R2*-UTE technique and HIC quantified by liver biopsy in subjects with iron overload. The liver biopsies will be obtained as indicated by good clinical management practice, and it is expected that most research participants who will receive the liver biopsy will have an inconclusive result by the R2*-GRE method. The iron quantification assessed in liver biopsies will be correlated with the R2*-UTE signals. If the correlation is sufficiently high, then a statistical model relating HIC by R2*-UTE and liver biopsy values will be established, as was done for R2*-GRE.³²

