9.1 Power and Accrual

Based on MRIRON study, we found that the correlation between R2*-GRE and HIC is 0.56 for patients with HIC > 15 mg Fe/g. The new R2*-UTE technique is expected to perform better for measuring high HIC values. Therefore, instead of testing if the r_{UTE} is different from zero, here we wish to test if the r_{UTE} is greater than 0.6. The one-sided testing hypotheses can be formulated as below: the null hypothesis $H_0: r_{UTE} \leq 0.6$ against the alternative hypothesis $H_a: r_{UTE} > 0.6$ we assume the true r_{UTE} to be 0.8. The study will be designed to have a significance level at $\alpha = 0.05$ and power at $1 - \beta = 0.8$. Although the parameter space for H_0 is large, to estimate the required sample size, we only need to consider the scenario that requires the largest sample size, which is: $H_0: r_{UTE} = 0.6$ v.s. $r_{UTE} = 0.8$. Based on a one-sided test, this design requires **41** liver biopsy samples.

We hope to accrue about 10-12 liver biopsies per year, so it will take approximately 4 years to achieve the desired sample size. Study subjects will be allowed to participate on the study only once in order to avoid potential bias introduced by repeat measurements on the same patient. There is a small chance that the liver biopsy specimen may be deemed inadequate due to technical sampling reasons. In this case, we will amend the protocol and continue patient accrual until we have obtained 41 evaluable liver biopsy specimens.

Approximately 20% of patients with iron overload have HIC values above 25 mg Fe/g, placing them in the category of massive iron overload. Because we aim at obtaining 41 liver biopsies for the analysis of the primary objective, we estimate that approximately 200 patients will undergo MRI testing with both R2*-GRE and R2*-UTE.

Healthy volunteers will be necessary for sequence development, and later for testing the robustness and repeatability of the UTE sequences. We estimate that approximately 35 healthy volunteers will be needed for sequence development and implementation.

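### The straight-line calibration and its 95% prediction bounds are provided for only when the same 41 pairs pass the 0.7 correlation rule, so lines reported through that rule are, on average, too steep with bounds too narrow

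*Combined protocol and SAP*

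**What the plan says.** Section 9.2 (primary objective) first explores the relationship graphically. If it looks linear, Pearson's correlation and its 95% CI are reported. The next step is conditional: "If the correlation is sufficiently high, i.e., the lower bound of the 95% CI exceeds 0.7, a simple linear regression model will be established". Prediction limits come with that model: "The 95% prediction bounds will be established". The Data Analyses part of the synopsis has the same rule, ending "a simple linear regression model will be established for the HIC prediction. The 95% prediction bounds will be established". Section 9.0 puts it in general terms: "If the correlation is sufficiently high, then a statistical model relating HIC by R2*-UTE and liver biopsy values will be established". A more complicated pattern goes to another suitable model, for which no correlation threshold is stated.

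The sample size in section 9.1 rests on a different criterion: "here we wish to test if the r_{UTE} is greater than 0.6", with "we assume the true r_{UTE} to be 0.8", and "Based on a one-sided test, this design requires 41 liver biopsy samples". Section 3.4 stops enrolment once the biopsies required by section 9.1 are in hand. No validation sample, cross-validation, bootstrap or shrinkage is described. The Study Design paragraph of the synopsis gives calibration of the technique as the aim.

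**The concern.** The correlation, the slope and the residual SD all come from the same pairs. A high sample correlation arises from a steep fitted slope, a small residual SD, or both. Reporting the line only after a high sample correlation therefore favours samples in which chance made the slope steep or the scatter small. Ordinary 95% prediction bounds take no account of that selection.

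The equation and its bounds are what the abstract puts forward as an alternative to biopsy for massively overloaded patients. Slope error matters most far from the mean, which is where those patients lie. The other side of the rule matters too: when it is missed, section 9.2 does not say that any line or bounds will be given, although the biopsies have been done and a line with wide bounds would still be informative.

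**Working it through.** **Inputs.** From section 9.1: null correlation 0.6, assumed true correlation 0.8, one-sided alpha 0.05, power 0.80, 41 pairs. From section 9.2: lower 95% CI bound above 0.7. Assumed, because the documents do not say: Fisher-z interval, normal errors with constant variance, biopsy HIC regressed on UTE, exactly 41 pairs.

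**The plan's own figure.** n = ((1.645 + 0.842) / (atanh 0.8 − atanh 0.6))² + 3 = (2.487 / 0.4055)² + 3 = 40.6, rounded up to 41. This reproduces section 9.1; power at 41 is 80.4%.

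**What the 0.7 rule requires.** The sample correlation must exceed tanh(atanh 0.7 + 1.96/√38) = tanh(0.867 + 0.318) = 0.829. This is above the planned true value of 0.8.

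**Effect of the rule on what is reported.** Simulation of 200,000 data sets of 41 bivariate normal pairs per true correlation, with least-squares fit and t-based 95% prediction bounds. The last three columns are averages over data sets that pass.

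| True r | Rule passed | Slope vs truth | Residual SD vs truth | Coverage of 95% bounds |
|---|---|---|---|---|
| 0.70 | 2.8% | +22% | −17% | 89.8% |
| 0.75 | 10.5% | +14% | −13% | 91.6% |
| 0.80 (plan) | 31.5% | +7.6% | −8.3% | 93.1% |
| 0.85 | 69.5% | +2.8% | −3.9% | 94.3% |
| 0.90 | 96.7% | +0.3% | −1.0% | 94.9% |
| 0.95 | 100% | 0% | −0.6% | 95.0% |

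Without the rule, the average slope equals the truth, the residual SD is 0.6% low (ordinary small-sample bias) and coverage is 95.0% in every row. With evenly spaced fixed UTE values instead of normal ones, the row for 0.80 becomes: passed 32.6%, slope +9.0%, residual SD −9.6%, coverage 92.8%.

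**How often a single line is affected.** At 0.80, the slope is above the truth in 77% of passing data sets, the residual SD is below it in 81%, and both hold in 59%.

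**Size in mg Fe/g.** The SD of HIC in the biopsied group is not given. For UTE 2 SD above its mean, the average slope error at a true correlation of 0.8 is 0.076 × 0.8 × 2 × SD. With an assumed SD of 10 this is 1.2 mg Fe/g; with the MRIRON SD of 6.8 (section 2.6, a less heavily loaded cohort) it is 0.8. The half-width of the bounds is roughly 2.02 × 0.6 × SD, that is about 12 and 8 mg Fe/g.

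**When the rule is missed.** At 0.80 this happens in 1 − 0.315, or about 68% of trials.

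**The case against.** Five points can be made for the plan.

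- **The effect at the planned value is modest.** A slope bias of 7.6% is smaller than the slope's ordinary sampling SD of about 12%, and 8% in the residual SD is smaller than its sampling SD of about 11%. The average error of 0.8 to 1.2 mg Fe/g sits inside bounds of about ±8 to ±12. The larger figures belong to true correlations at which the rule seldom passes. This stands, and it limits the weight of the point.
- **Always fitting does not repair a passing trial.** Its slope, residual SD and bounds are the same with or without the rule. The 95.0% is an average that includes trials that miss the rule. This also stands, so the fix needs a second part.
- **The text does not forbid a model after a miss.** Section 9.2 is silent on that case, the correlation and its CI are reported for any linear pattern, and the non-linear branch carries no threshold. So a weak result would not be hidden. What stands is narrower: the linear branch provides for no line and no bounds after a miss.
- **Withholding an equation when the correlation is weak is a defensible safeguard.** Restricting the claim gives the same protection without restricting the report.
- **Much of the bias follows from the mismatch between rule and sample size.** This is right. With the one-sided 0.6 test at 41 pairs, 82% pass, the slope bias is +2.5% and coverage is 94.7%. With the 0.7 rule and about 150 pairs, which gives it 80% power, the slope bias is +1.4% and coverage 94.8%.

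A reader might go further and infer that whatever line this study publishes is too steep with bounds too narrow. The documents do not support that. The bias is an average over passing samples, both errors occur together in only 59% of them at the planned value, and the effect is negligible if the true correlation is about 0.9 or more. Section 2.6 reports 0.96 to 0.98 for GRE over the full MRIRON range; section 9.1 reports 0.56 for GRE above 15 mg Fe/g and plans on 0.8 for UTE. The documents therefore do not settle which row of the table applies.

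**Conclusion.** The point holds as a statement about the reporting procedure. At the plan's own correlation of 0.8, lines that come through the 0.7 rule have, on average, a slope about 8% too steep and a residual SD about 8% too small, and their 95% bounds cover about 93%. Below 0.8 the bias grows, while the rule passes less often; from about 0.9 it is negligible. These sizes rest on normal, constant-variance errors, a Fisher-z interval and 41 pairs. At 0.8 the more frequent consequence is the other one: in about 68% of trials the linear branch provides for no calibration, although calibration is the stated aim. The matter is worth correcting because the correction is nearly free, not because the bias at the planned value is large.

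**What to change.** In section 9.2 and the synopsis, and in matching terms in section 9.0:

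1. When the pattern is linear, fit the regression of biopsy HIC on UTE and report slope, residual SD and 95% prediction bounds whatever the correlation. Use the correlation criterion only to decide whether a claim is made. This ends selective reporting and ensures a calibration for any linear pattern.
2. If a claim is made, report a bootstrap optimism assessment that repeats the correlation rule in each resample, and state that ordinary bounds are somewhat optimistic after a pass. The bootstrap is a guide only. Passing samples at a true correlation of 0.8 average 0.858, so resampling from them reflects a bias nearer the 0.85 row of the table than the 0.80 row and will tend to understate it.
3. Reconcile the 0.7 rule in section 9.2 with the 0.6 test that section 9.1 was sized for. Most of the bias goes once rule and sample size agree.

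Items 1 and 2 cost a few sentences, a little more analysis and no new data. The downside is that an equation with wide bounds appears when the correlation is modest. Item 3 needs no new data if the criterion is brought to 0.6; keeping 0.7 with 80% power would need about 150 biopsies: ((1.960 + 0.842) / (atanh 0.8 − atanh 0.7))² + 3 = 149.7.

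### The 80% power belongs to a one-sided test of r > 0.6, but the written criterion is a 95% CI lower bound above 0.7, which has about 30% power at the assumed r = 0.8 with 41 biopsies

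*Combined protocol and SAP*

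**What the plan says.** Section 9.1 (Power and Accrual) gives a formal hypothesis: "here we wish to test if the r_{UTE} is greater than 0.6". For the alternative, "we assume the true r_{UTE} to be 0.8". The significance level is 0.05 and the power 0.8. "Based on a one-sided test, this design requires" 41 biopsies. Inadequate specimens are to be replaced; the plan is to "continue patient accrual until we have obtained 41 evaluable liver biopsy specimens". Section 3.4 stops enrollment once the Section 9.1 biopsy count is reached.

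Section 9.2 (Statistical Analysis) describes the primary analysis. The relationship is first examined graphically. If it looks linear, Pearson's correlation and its 95% confidence interval are reported, and if "the lower bound of the 95% CI exceeds 0.7, a simple linear regression model will be established for the HIC prediction". The synopsis (Data Analyses) carries the same rule. Neither place mentions 0.6 or a one-sided test, and neither says whether the interval is one- or two-sided.

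Section 9.0 shows what the rule is for: "If the correlation is sufficiently high, then a statistical model relating HIC by R2*-UTE and liver biopsy values will be established".

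**The concern.** The sample size and the decision rule refer to different tests. The rule in Section 9.2 moves the threshold from 0.6 to 0.7. If the interval is the usual two-sided one, it also moves the one-sided error rate from 0.05 to 0.025. Both changes make the criterion harder to meet. The plan does not explain the change and gives no power for the 0.7 rule.

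A biopsy-calibrated prediction of HIC is what the study sets out to deliver. Under the linear plan it is built only if the 0.7 rule is met, so the probability of meeting that rule is the power that matters. Two unreconciled thresholds also leave room to choose the success criterion after the data are seen.

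**Working it through.** **Inputs.** From Section 9.1: null correlation 0.6, true correlation 0.8, one-sided alpha 0.05, power 0.80, n = 41 evaluable biopsies. From Section 9.2: threshold 0.7 and a 95% confidence interval. The interval is taken as two-sided by convention, and the one-sided reading is shown as well.

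**Method.** Fisher's z for a single correlation, with standard error 1/√(n − 3):

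- n = [(z_alpha + z_power) / (atanh r1 − atanh r0)]² + 3
- power = Φ[(atanh r1 − atanh r0) × √(n − 3) − z_alpha]

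The transformed values are atanh 0.6 = 0.693, atanh 0.7 = 0.867 and atanh 0.8 = 1.099. For n = 41, √38 = 6.164.

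**Step 1: reproduce the plan's figure.** n = [(1.645 + 0.842) / (1.0986 − 0.6931)]² + 3 = 40.6, so 41. Power at 41 is Φ(0.4055 × 6.164 − 1.645) = 80.4%. The stated sample size is right for the stated test. A two-sided version would give 51, so 41 is the one-sided figure.

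**Step 2: power of the written rule at n = 41, true r = 0.8.** The difference is 1.0986 − 0.8673 = 0.2313.

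- Two-sided 95% interval: Φ(0.2313 × 6.164 − 1.960) = Φ(−0.534) = 29.7%
- One-sided 95% bound: Φ(0.2313 × 6.164 − 1.645) = Φ(−0.219) = 41.3%

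A bivariate-normal simulation with 400,000 replicates gave 31.7% and 43.7%.

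**Step 3: separate the two changes.** With the threshold left at 0.6 and only the interval made two-sided, power is Φ(0.4055 × 6.164 − 1.960) = 70.5%. Most of the loss therefore comes from raising the threshold to 0.7.

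**Step 4: the observed correlation needed.**

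- Section 9.1 test: tanh(0.693 + 1.645/6.164) = 0.744
- Section 9.2 rule, two-sided interval: tanh(0.867 + 1.960/6.164) = 0.829
- Section 9.2 rule, one-sided bound: tanh(0.867 + 1.645/6.164) = 0.812

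An observed correlation between 0.744 and 0.829 passes the Section 9.1 test and fails the Section 9.2 rule. At true r = 0.8 this happens with probability 80.4% − 29.7% = 50.7%.

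**Step 5: what the 0.7 rule would need for 80% power.**

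| | Two-sided 95% CI | One-sided 95% bound |
|---|---|---|
| Biopsies at true r = 0.8 | 149.7, so 150 | 118.6, so 119 |
| True r at n = 41 | 0.867 | 0.854 |

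**Step 6: sensitivity to the true correlation (n = 41, 0.7 rule).**

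| True r | Two-sided 95% CI | One-sided 95% bound |
|---|---|---|
| 0.80 | 29.7% | 41.3% |
| 0.85 | 66.9% | 77.4% |
| 0.90 | 96.2% | 98.1% |

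**The case against.** The strongest reply is that the 0.7 rule is a gate to modelling, not the hypothesis test. Section 9.1 states the hypotheses and error rate, and it belongs to the same chapter as Section 9.2. One could read the plan as two steps: test against 0.6, then require a stricter result before building a model meant to replace biopsy. The 80% would then still describe the test. This reading is possible, but no text sets it out. Section 9.2 contains no test against 0.6, and the power of the gate would still be unstated.

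A second reply is that missing the bound need not leave the study without a calibration. The plan does not say what follows a miss, the branch for non-linear patterns has no correlation threshold, and the abstract says without condition that the cohort data will be used for modelling. The first part stands: the documents do not forbid a model after a miss. But the non-linear branch does not cover a linear relationship that falls short of 0.7, and for that case Section 9.2 provides nothing.

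A third reply is that the true correlation may exceed 0.8. Section 2.6 reports 0.96–0.98 for R2*-GRE against biopsy over the full range of the earlier study, and Section 9.2 sets no HIC floor. If the biopsied group spans a wide range, power could be much higher, as Step 6 shows. However, 0.8 is the plan's own design value. Section 9.1 gives 0.56 for R2*-GRE above 15 mg Fe/g, and Section 9.0 expects most biopsied participants to have inconclusive R2*-GRE results.

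**Conclusion.** The concern holds. The sample size of 41 is correct for the test in Section 9.1, but the stated 80% power does not apply to the only criterion written for the primary analysis. At the plan's own true correlation of 0.8, that criterion has 29.7% power with a two-sided 95% interval and 41.3% with a one-sided bound. Neither reading brings it back to 80%. If R2*-UTE performs exactly as assumed, the study will more likely than not miss its written condition for building the linear calibration model.

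The figures assume bivariate normality, 41 evaluable biopsies, a linear relationship, and true r = 0.8. They improve quickly if the true correlation is higher.

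**What to change.** State one rule, in the same words, in Sections 9.1 and 9.2 and the synopsis, including the sidedness of the interval. The documents do not show which threshold is intended, so the sponsor has to choose:

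- **Align with Section 9.1.** Success is a one-sided 95% lower confidence limit for the correlation (the lower limit of the two-sided 90% interval) above 0.6. Power is 80% at 41 biopsies and true r = 0.8. The price is a lower bar as evidence for the technique.
- **Keep the 0.7 rule.** State its power in Section 9.1: about 30% at r = 0.8 with a two-sided interval, reaching 80% only if r is about 0.87. The price is a less favourable stated power.
- **If two steps are intended,** say so, and give the power of each step.

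All three are changes of wording and need no extra patients. Only keeping 0.7 with 80% power at r = 0.8 would change the size of the study, to about 150 biopsies. At the planned 10–12 per year that is 150/12 = 12.5 to 150/10 = 15 years, against about 4 planned.

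Section 9.2 should also say what is reported when the relationship is linear but the criterion is missed. Reporting the fitted line and its prediction bounds whatever the result would be a sensible addition, though reconciling the two sections does not depend on it.

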Figure 2 shows the 95% confidence interval for the T2* fit derived from the precision calculations and overlaid on the Bland–Altman plot in Fig. 1B. The simulation (red curve) shows that there is a nonlinear change in precision. This change is not easily recognized in the low to moderately iron-overloaded population (<15 mg/g), and therefore may have been missed by other investigators. The simulation confirmed our experimental observation of a large imprecision for higher iron overload with the standard R2*-GRE method. Other researchers have reported higher HIC values using standard R2*-GRE, but these data points demonstrated larger errors or deviated from the linear regression line.^{16;59} Interpretations of these findings focus on the multi-exponential signal decay or nonlinear relationship between HIC and R2*-GRE, respectively, in highly overloaded areas of the liver.⁵⁹ Because the results of our fit precision simulations and experimental data are in concordance, we conclude that the fit imprecision at

higher HIC is the major source of inaccuracy between HIC and R2*-MRI while measuring iron overload in patients; other potential sources of error may be negligible.

Our simulation model gives the upper limit on the R2* fit precision obtained with a specific MR sequence (e.g., R2*-GRE). With the proposed R2*-UTE sequence, which yields optimized precision for high R2* values too, we can characterize other potential factors impacting the correlation between HIC and R2*. Although multi-exponential or nonlinear behavior cannot be ruled out by using current methods, a more accurate quantification of large R2* species can help determine the true correlation between HIC and R2*-MRI and ultimately the distribution of hepatic iron stores in patients with massive iron deposition.

[figure not shown]

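### Section 9.2 takes its 95% prediction bounds from a constant-spread regression with no check on residual spread, although the protocol's own precision model has UTE error growing with HIC

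*Combined protocol and SAP*

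**What the plan says.** Section 9.2 first plots UTE-based HIC against biopsy HIC. If the plot looks linear and the lower 95% confidence limit for Pearson's correlation exceeds 0.7, "a simple linear regression model will be established for the HIC prediction. The 95% prediction bounds will be established". The synopsis repeats the rule ("The 95% prediction bounds will be established"). The alternative route reads "If more complicated pattern shown graphically, appropriate model will be developed to describe the relationship". Neither place names a residual plot, a variance check, weighting or a transformation. Section 9.0 describes the product as "a statistical model relating HIC by R2*-UTE and liver biopsy values will be established, as was done for R2*-GRE".

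On the expected error, Section 2.7 says of the GRE simulation that it "shows that there is a nonlinear change in precision". It attributes most of the inaccuracy at high iron to imprecise curve fitting and regards other sources as possibly minor. The Figure 2 legend gives UTE a narrower flare than GRE, but still a flare.

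On who will be biopsied, Section 9.0 says "it is expected that most research participants who will receive the liver biopsy will have an inconclusive result by the R2*-GRE method". Section 9.1 bases the screening number on "Approximately 20% of patients with iron overload have HIC values above 25 mg Fe/g". For planning, "we assume the true r_{UTE} to be 0.8".

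**The concern.** A straight-line relationship whose residuals fan out passes the linearity condition and goes directly to constant-width bounds. The protocol's own precision model predicts a fan of this kind, and Section 9.2 does not carry it forward.

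The bounds tell a user how far to trust a single UTE reading. If spread grows with HIC, they are too narrow at the top of the range and slightly too wide nearer 25 mg Fe/g. The top of the range is where the study aims to replace biopsy. Errors in the two directions largely cancel in the average, so an overall coverage figure would look right.

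**Working it through.** **1. Planned figures.** For a null correlation of 0.6, a true value of 0.8, one-sided alpha 0.05 and power 0.80, Fisher's z gives n = ((1.645 + 0.842)/(1.0986 - 0.6931))^2 + 3 = 40.6, so 41 as in Section 9.1. At n = 41 the gate needs an observed r of tanh(atanh 0.7 + 1.96/sqrt(38)) = 0.829.

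**2. Precision model (Section 2.7).** The signal is S0 exp(-TE x R) plus an offset, with SNR 50. GRE has 20 echoes from 1.1 ms in 0.8 ms steps. Each echo contributes the row [exp(-TE x R), -S0 TE exp(-TE x R), 1], and the covariance is the inverse of J'J. The anchors in Section 2.3 (500 Hz at about 15, 900 Hz at about 25) give R = 40 x HIC - 100 Hz, so SD(HIC) = SD(R)/40.

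The Figure 2 settings for UTE (21 echoes, first at 0.05 ms) can be read two ways: (A) the GRE echoes plus one at 0.05 ms, or (B) 21 echoes from 0.05 ms in 0.8 ms steps. A third row assumes 0.25 ms spacing.

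| UTE fit SD (mg Fe/g) at HIC | 15 | 25 | 40 | 50 | 60 |
|---|---|---|---|---|---|
| Reading A | 0.47 | 0.99 | 2.3 | 3.8 | 6.0 |
| Reading B | 0.47 | 0.98 | 2.0 | 3.0 | 4.4 |
| 0.25 ms (assumed) | 0.71 | 0.91 | 1.5 | 2.0 | 2.5 |

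The GRE/UTE ratio is 2.1 at HIC 20, and 4.3 (A) or 4.85 (B) at 40. The Figure 2 legend states 2 and 4, so this is essentially the protocol's model. From 25 to 40 the SD rises 2.3/0.99 = 2.3-fold (A) or 2.0/0.98 = 2.0-fold (B).

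**3. Coverage of ordinary 95% bounds.** Simulated studies of 41 biopsies regressed biopsy HIC on the UTE reading, and only studies passing the gate were kept. Assumptions that are not in the documents:
- HIC is 25 plus an exponential tail with mean 10, cut at 61.3 (the SWiTCH maximum in Table 1). This puts about 8 of 41 biopsies at or above 40.
- All other error has a constant SD of 1, 2 or 5 mg Fe/g.

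For scale, the pooled MRIRON residual SD is 6.8 x sqrt(1 - r^2). This is 1.4 at r = 0.98 and 1.9 at r = 0.96. It already contains GRE fit error and comes from a mean HIC of 10.9, so SD 1-2 is a low-end case.

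| Other-error SD | r | Coverage at HIC 40 or more | Half-width at predicted 50: given / needed |
|---|---|---|---|
| 1 | 0.96-0.97 | 80-82% | 4.2-4.6 / 6.3-7.4 |
| 2 | 0.94-0.95 | 85-88% | 5.6-6.0 / 7.2-8.0 |
| 5 | 0.82 | 90-92% | 10.6-10.7 / 11.5-12.0 |

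Coverage over all HIC of 25 or more is 94-95%. At HIC 25-40 it is 97-98% for SD 1-2.

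**4. What belongs to the gate.** At SD 5 only 46-52% of studies pass, and passing favours small residuals. With fit variance divided by 100, so that spread is nearly constant, gated coverage above 40 is already about 94%. Of the shortfall at SD 5, about 1 point is therefore selection and 2-4 points are unequal spread.

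**5. Sensitivity, coverage above 40.**
- 0.25 ms spacing: 88-93%.
- Fit variance divided by 10: 89-94%; divided by 100: 94-95%.
- Other HIC shapes above 25 (tail mean 6 or 15, or uniform 25-60): 76-92% at SD 1-2 and 89-94% at SD 5.
- HIC mixes that extend below 25: 72-89% at SD 2, 86-91% at SD 4 and 93-94% at SD 8.

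**The case against.** The strongest reply is that the effect is small at the protocol's own planning value. That stands: near r = 0.8 unequal spread costs about 2-4 points. The 80-88% figures need r of about 0.94-0.97. Section 2.7's view that other errors may be minor points that way, but nothing in the documents establishes it.

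Second, the error curve is illustrative. Figure 2 keeps the GRE settings apart from the first echo, Section 4.2 does not fix UTE echo times, and patient values are ROI readings, so averaging over voxels could shrink the fit error. This also stands as uncertainty. Against it, Section 2.7 overlays the unaveraged curve on patient-level MRIRON data and finds the two in agreement. The uncertainty is a reason to check the spread, not to assume it constant.

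Third, an analyst might treat a fan as a more complicated pattern under the fallback. That is a possible reading, but the clause speaks of describing the relationship and states no action on spread.

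A reader might also infer a four- to six-fold rise in error across the planned biopsy range, by running the table from 25 to 60. The documents give no upper limit of 60 for the biopsied group. Under the assumed tail only about 6% (about 2 of 41) exceed 50. The rise from 25 to 40 is about two-fold.

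**Conclusion.** The point holds in a limited form. Followed as written, and if the protocol's precision model applies to patient readings, Section 9.2 yields nominal 95% bounds that are too narrow at the highest HIC. Coverage above 40 mg Fe/g is about 80-88% when other error is small and about 91-92% near the planned correlation. The direction follows from the protocol's own model. The size depends on the assumed HIC tail, the assumed other-error SD, the echo settings and the amount of ROI averaging. The cut at 40 is a choice made for this check, not a figure in the documents.

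A reader might go further and infer that the bounds are certainly invalid or that the primary objective is compromised. The documents support neither. The patient-level UTE error is unknown, and the sample size, the 0.7 gate and the association objective do not depend on this point. The weight is minor, and confidence in the size is moderate.

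**What to change.** In Section 9.2 and the synopsis, prespecify a plot of residuals against predicted HIC together with one trend rule named in advance, such as a one-sided Spearman test of absolute residuals at 0.10.
- **If spread increases:** take the 95% prediction bounds from a regression with SD modelled as a function of predicted HIC, or from a log-scale model, and show the simple-regression bounds alongside.
- **If it does not:** keep simple regression as primary and show the variance-modelled bounds as a sensitivity analysis, because the check has low power at n = 41.

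Do not require coverage by HIC stratum, or label it descriptive only. A stratum below 25 may be nearly empty, and about 8 patients above 40 cannot separate the possibilities: all 8 are covered with probability 0.95^8 = 66%, 0.91^8 = 47% or 0.85^8 = 27%.

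The cost is analysis wording and one extra variance parameter, with no new data. Bounds at high HIC become wider. Correction is partial: with the example rule, coverage above 40 moves from 80-88% to about 87-90% at SD 1-2 (triggered in 31-65% of studies). At SD 5 it reaches about 92%, a gain of about 1 point or less (triggered in 15-18%). With truly constant spread the rule triggers in 9% and coverage stays at 95%. Making the variance model mandatory is less attractive, since it lowers coverage above 40 from 95% to 91-92% when spread is constant.
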